forearm. The participant will click a mouse when they feel the thermode temperature change from neutral to warm and then hot to painful. The pressure pain threshold will be measured by electronic pressure algometer (Somedic Sales AB, Hörby, Sweden. Participants will press a control button when they experience the first sensation of pain. The reactivity and habituation assessment will take place at 1pm. The cold pressor test (CPT) will be administered 3 times. As detailed under procedures, participants will be instructed to immerse their hand in ice-cold water kept at 3 degree C, for a duration of 1min. the interval between the three cold pressor tests will be 1.5 hours. Blood will be sampled after the 1st, 2nd, and 3rd cold pressor test twice, 20min and 50min after hand removal from the cold water bath (these timepoints have been shown sensitive to capture increases of cortisol and IL-6). Urine will also be collected during and after the administration of the cold pressor test series, starting at 1pm and closing out at 6pm.. Prior to, during, and after the cold pressor series, participants will rate their stress levels as well as the unpleasantness of the cold sensation induced by the CPTThe final pain modulation tests, temporal summation and conditioned pain modulation will occur at 500pm. Temporal summation of pain is frequently used as an index of central sensitization of dorsal horn neurons⁵⁶, and will be assessed using the Somatosensory Analyzer (Medoc, Minneapolis, MS). The participant wil have the thermode placed on forearm volar skin of the arm not used for blood draws. Four sequences each consisting of ten brief consecutive heat pulses will be applied via a thermode with a pulse-to-pulse interval of 2.5 sec. Conditioned pain modulation assesses the principle of 'pain inhibits pain', and is a measure of the pain-inhibitory capacity of the central nervous system. The participant will have the thermode placed on the forearm volar skin not used for blood draws...For the test, the test stimulus will be the TS sequence at highest tolerable temperature, applied to the outer volar surface of the non-dominant forearm, along C8-T1 innervations. Immersion of the contralateral foot into a painfully hot water bath (47 °C, Techne® water baths, Bibby Scientific US, Burlington, NJ) Prior to discharge, participants will receive a dinner shortly after 6pm.

Procedures:

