Polysomnographic recording (PSG). Sleep will be recorded using the Embla system N7000 (Medcare US, Buffalo) on the screening night visit to ensure that participants are free from sleep disorders (clinical interview will be used to diagnose insomnia disorder and also to support the diagnoses of other sleep disorders, such as nightmare disorder, circadian rhythm disorder).

Blood Sampling. Blood samples will be drawn at intermittent intervals during the experimental visit using an indwelling 18-gauge forearm catheter from 1pm to 7pm. The total amount of blood taken will not exceed 200ml.

IL-6 will be measured in plasma in our laboratory, using a high sensitivity enzyme immunosorbent assay (ELISA, Quantikine ® HS, R&D Systems, Minneapolis, MN). IL-6 will be measured at baseline, after each cold pressor test, and hourly after the last cold pressor test until 7pm.

PGE2 metabolite will be measured in urine collected during the cold pressor test series (from 3-7pm). Urinary PGE2 will be analyzed in our lab using an EIA (Cayman Chemical, Ann Arbor, MI), and levels will be adjusted for urinary creatinine levels.

Cortisol will be measured in plasma and assayed in the Harvard Catalyst Central Lab, using the Access Chemiluminescent Immunoassaay (Beckman Coulter Fullerton, CA). Cortisol will be measured at baseline, after each cold pressor test, and hourly after the last cold pressor test until 7pm.

Glucocorticoid (GC) sensitivity will be assessed in vitro by examining the capacity of monocytes to produce IL-6 in response to the synthetic glucocorticoid dexamethasone (DEX). In brief, whole blood will be incubated with LPS (100 pg/ml) in the presence of different concentrations of DEX (0-400nM). After incubation with fluorescence-conjugated antibodies (CD14, CD45, IL-6), monocyte expression of IL-6 will be measured in the Flow Cytometry Core at the BIDMC (Gallios[™], Beckman-Coulter Inc). This protocol was developed by the PI for our currently ongoing study on pattern of repeated sleep restriction and recovery (R01 HL 105544). Lower IL-6 expression in response to DEX would indicate

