Twenty sec after foot immersion into hot water bath (47 °C, the conditioning stimulus that is supposed to activate descending pain-inhibitory circuits), the participant rates the intensity of heat pulses (test stimulus, individually tailored to highest tolerable temperature) applied to the forearm.

inhibitory circuits and thereby decrease the perceived pain of the forearm test stimulus (see **Figure 2** for setup).

In total, four CPM trials will be performed: two trials using a hot water bath (47 °C) and two baseline trials without a water bath. For each hot water bath trial, the participant's foot will be first submerged in the water bath. After 20sec of immersion, the 10-pulse temporal summation sequence will be applied to the forearm and the participant will be prompted to rate the pain intensity of the 1st, 4th, 7th, and 10th stimulus using the VAS. There will be a two-minute rest period between all trials during which the thermode will be systematically moved from the distal to proximal sites along the C8-T1 innervated skin in order to avoid re-stimulation of the previously sensitized skin. For statistical analysis, ratings of the two 10-pulse sequences under the conditioning stimulus (hot water) will be averaged, and contrasted against ratings from the baseline (no-water) condition. A decrease in pain intensity ratings under the hot water condition compared to the no-water condition will be used as an index of the pain-inhibitory capacity.

B. Statistical Considerations

Sample Size Justification: For sufficient statistical power, we will need to have 20 participants with a diagnosis of insomnia disorder (based on DSM-V criteria), and 20 healthy control sleepers complete the study protocol (60% women, see power calculation below).

Power calculation

Power calculations were performed for the primary objective of this proposal. With respect to the proposed stronger **inflammatory response reactivity** in insomnia compared to healthy controls, power calculations were based on findings from Heffner et al.¹⁶, reporting a difference in the IL-6 response between poor and good sleepers to an acute challenge of 1.6 pg/ml (SD 1.71 pg/ml, estimated from graph). Thus, we need to study **20 participants in each group** to reach optimal power of 80% (unpaired t-test, alpha = 0.05).

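### The painful 5pm tests fall inside both stated challenge-urine windows, so urinary PGE2 may reflect a second stressor as well as the cold pressor test

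*Combined protocol and SAP*

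**What the plan says.** B1 names IL-6 and PGE2 as the inflammatory markers of the primary objective and defines both as responses to the cold pressor test (CPT).

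B3.A, 1-Day CRC Visit, places the "final pain modulation tests, temporal summation and conditioned pain modulation will occur at 500pm". The same description covers the challenge urine: "Urine will also be collected during and after the administration of the cold pressor test series, starting at 1pm and closing out at 6pm". The PGE2 paragraph under Procedures gives a different window, "urine collected during the cold pressor test series (from 3-7pm".

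The 5pm session is painful by design. Under Modulation testing details, temporal summation has four ten-pulse heat sequences at a temperature adjusted to what each person tolerates. Conditioned pain modulation adds four more ten-pulse sequences: "two trials using a hot water bath (47 °C) and two baseline trials without a water bath". The visit description introduces the conditioning stimulus as "Immersion of the contralateral foot into a painfully hot water bath".

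For blood, Procedures states: "IL-6 will be measured at baseline, after each cold pressor test, and hourly after the last cold pressor test until 7pm". The cortisol schedule is the same. The Statistics paragraph in B3.B names only baseline and the post-testing measures after the first, second and third CPT as time points.

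No section calls for a void at 5pm, a separate assay of urine from before and after the tests, or any handling of the pain tests in the analysis.

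**The concern.** A urine specimen accumulates whatever happens during its collection. If the PGE2 specimen spans the CPT series and a later set of painful heat tests, its value is a response to both, whereas the primary objective concerns the CPT alone.

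The tests would do no harm to the group comparison if they raised PGE2 equally in both groups. The plan gives two reasons not to assume this. Its own hypothesis is that people with insomnia react more strongly to a stressor. The heat temperature is also set individually, so the delivered stimulus may differ between groups.

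Unlike a timed blood draw, a specimen that mixes the two periods cannot be divided afterwards, and the planned creatinine adjustment does not separate one stressor from another.

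**Working it through.** **The plan's own figure.** The only figure that can be reproduced is the sample size, which covers IL-6 and cortisol but not PGE2. With a two-sided alpha of 0.05 (sidedness is not stated) and an unpaired t-test:
- IL-6: standardised difference 1.6/1.71 = 0.94; 19 per group for 80% power; power 82% at 20 per group.
- Cortisol: 10/11 = 0.91; 20.0 per group; power 80.0% at 20 per group.

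The stated 20 per group is reproduced, and the point below does not depend on it.

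**Step 1: urine windows against 5pm.** Share of clock time from 5pm on = (end − 17:00)/(end − start).
- 1–6pm (visit description): (18 − 17)/(18 − 13) = 1/5 = 20%.
- 3–7pm (PGE2 paragraph): (19 − 17)/(19 − 15) = 2/4 = 50%.

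5pm is inside both, so choosing one window does not remove the overlap.

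**Step 2: how long the tests last.** Ten pulses at 2.5 s take 25 s, and rests are 2 min.
- Temporal summation: 4 × 25 + 3 × 120 = 460 s.
- Conditioned pain modulation: two hot-water trials at 20 + 25 = 45 s and two dry trials at 25 s, so 2 × 45 + 2 × 25 + 3 × 120 = 500 s.
- Total: 960 s = 16 min, or 18 min with a 2-min gap between the two tests.

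Without set-up, the tests end near 17:20. That leaves about 40 min of a 1–6pm window, or about 100 min of a 3–7pm window.

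**Step 3: the added stimulus.** At most (4 + 4) × 10 = 80 pulses and 2 × 45 = 90 s of hot-water immersion, against at most 3 × 60 = 180 s of cold immersion. Both are upper limits: one temporal summation sequence is a practice trial, participants may stop the heat, and they may withdraw the hand early from the cold bath.

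**Step 4: blood samples.** The first CPT is at 1pm. The interval is 1.5 h in the visit description and 60 min in the CPT paragraph under Procedures. Allow 1 min of immersion, then add 20 and 50 min.

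| Interval | CPT times | Last 50-min sample | 20/50-min samples after 5pm |
|---|---|---|---|
| 60 min | 13:00, 14:00, 15:00 | 15:51 | 0 of 6 |
| 90 min | 13:00, 14:30, 16:00 | 16:51 | 0 of 6 |

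Only the hourly samples at about 6pm and 7pm clearly follow the tests; the one at about 5pm is borderline. The Statistics paragraph does not name these as time points.

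**Step 5: when the overlap biases the comparison.** Under a simple additive model, the observed group difference in challenge-urine PGE2 equals the difference due to the CPT plus the difference due to the pain tests. A pain effect common to both groups cancels; only a difference between groups remains.

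The documents give neither a PGE2 variance nor a pain effect, so the following is purely an assumption. With no true CPT difference, 20 per group and a two-sided 0.05 t-test, a group difference caused only by the pain tests would give a significant result this often:
- 0.2 SD: about 9% of trials
- 0.5 SD: about 34%
- 0.8 SD: about 69%

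**The case against.** Both groups undergo the same tests at the same hour, so the comparison is not biased merely because the tests occur. That stands. A reader might infer that no PGE2 group difference could be attributed to the CPT. The documents do not support this, since bias needs a differential response and they give no figure for one. Individual tailoring can also be read as equalising perceived intensity rather than creating imbalance, and the cold exposure itself is not identical between people.

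A reader might also infer that the primary IL-6 and cortisol results are contaminated. They are not: step 4 shows that every 20- and 50-minute sample precedes 5pm under either interval, and no recovery analysis is planned. Whether a 7pm sample exists is itself unclear, because the visit description ends urine collection at 6pm, with dinner shortly afterwards and then discharge.

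Two further inferences go too far. The 20% and 50% are shares of time and do not measure contamination. Nor do the documents say that the afternoon's urine is pooled into one specimen. Serial voids are possible, but no separate use of them is planned.

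Finally, pain-threshold tests at 11am fall within the baseline period, which lasts until 12pm, so baseline is not free of pain stimuli either. This does not offset the problem: threshold tests stop at first pain, whereas the conditioned pain modulation stimulus uses the highest tolerable temperature.

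**Conclusion.** The point holds for urinary PGE2 only. Under either stated window the plan allows a second painful stressor into the specimen meant to show the response to the CPT, and nothing separates the two. The overlap is certain from the stated times. Its effect on the group comparison is possible but of unknown size, and depends on the groups responding differently to the 5pm tests. The study's own hypothesis makes that assumption hard to dismiss.

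The planned IL-6 and cortisol reactivity and habituation contrasts stand. Late hourly samples are exposed, but they enter no named analysis. The change is worth making because a marker of the primary objective is involved, the remedy is cheap, and mixed urine cannot be separated later.

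**What to change.** 1. Reconcile the two urine windows and the two CPT intervals. The challenge-urine window should start no later than the first CPT, because a 3pm start opens after it and cannot by itself supply the post-first-CPT value that the Statistics paragraph calls for.
2. Collect a void immediately before the 5pm tests, and keep any later urine as a separate specimen.
3. State in the 1-Day CRC Visit description, the PGE2 paragraph and the Statistics paragraph that the PGE2 response to the CPT uses only the specimen from before the tests.
4. State that any use of blood or blood pressure values obtained after the tests begin will be labelled as following the pain tests.

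The cost is one additional void, a few sentences and a shorter PGE2 window. From a 1pm start the window becomes 1–5pm, 4 h. It leaves about 1 h after the third CPT if the interval is 90 min, or about 2 h if it is 60 min. The documents give no time course for urinary PGE2, so the team should consider whether that is enough. Moving the pain tests after the last specimen would not be equivalent: it keeps the full window, but with a 7pm close it delays the tests by about two hours. The change does not address the 11am threshold tests within baseline.

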a higher GC sensitivity and this mechanism may contribute to the proposed stronger inflammatory reactivity in insomnia disorder. Measures will be performed once at baseline, using the 2pm blood. Autonomic markers: Blood pressure (BP) measurements will be collected during baseline, throughout the testing sessions and recovery period of the experimental visit, using the dinamap system. Physiological stress challenge - cold pressor test (CPT): A trial CPT will be administered during the initial screening to identify any previously-unrecognized incidence of Raynaud's phenomenon or inability to tolerate the ice bath. The CPT will be administered three times during the experimental visit, starting at 1pm. Throughout the testing and recovery period (until 6pm), the participant will remain in a seated position in a comfortable chair. The CPT will be performed using the hand/arm that is not being used for blood sampling in order to prevent interference. A series of three CPT tests will be applied with an inter-test interval of 60min. Repeated administrations of the cold pressor test have been performed in previous studies (with intervals as short as 2min^{8;13}), but without investigating system's responses. For the current study purposes, an inter-test interval of 60 min has been chosen to capture response increases of IL-6 and cortisol^{8;9;16}. For each CPT test, participants will be asked to insert their hand in a temperature-controlled water bath (Techne® water baths, Bibby Scientific US, Burlington, NJ), kept at 3 degree C, and instructed to leave their hand in for a duration of 1min (participants are told that they can take their hand out earlier if the sensation is getting unbearable). Blood will be drawn 20 and 50min after hand removal from the cold water bath. These time points have been shown sensitive to capture peak cortisol levels as well as significant IL-6 increases^{8;9;16}. Participants will rate the unpleasantness of the sensation prior to hand immersion into the cold water bath, and continue with ratings at 10sec intervals during and after the testing period (up to 3min posttestina).

Pain threshold testing details:

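### PGE2 urine has two conflicting collection windows (1–6pm and 3–7pm), and one series urine cannot supply the time levels of the stated models

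*Combined protocol and SAP*

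**What the plan says.** **Role of PGE2.** Section B1 names IL-6 and PGE2 as the inflammatory markers expected to respond more strongly in insomnia. Secondary objective 1 in B1 expects inflammatory habituation over repeated CPTs, and B2 plans to measure the inflammatory response to every challenge.

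**Urine.** The 1-Day CRC Visit text in B3.A includes urine for prostaglandin in the baseline assessment. For the challenge it says: "Urine will also be collected during and after the administration of the cold pressor test series, starting at 1pm and closing out at 6pm". Under Procedures in B3.A, the PGE2 "metabolite will be measured in urine collected during the cold pressor test series (from 3-7pm"), with creatinine adjustment. IL-6 and cortisol are to be measured in plasma at baseline and following every CPT; nothing similar is said for PGE2.

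**Timetable.** The visit text says "The reactivity and habituation assessment will take place at 1pm" and "the interval between the three cold pressor tests will be 1.5 hours". The CPT paragraph under Procedures says "The CPT will be administered three times during the experimental visit, starting at 1pm" and "A series of three CPT tests will be applied with an inter-test interval of 60min". It also says "Blood will be drawn 20 and 50min after hand removal from the cold water bath". For glucocorticoid sensitivity, Procedures says "Measures will be performed once at baseline, using the 2pm blood".

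**Models.** In B3.B the primary mixed model has two time levels: baseline and after the first CPT. The habituation model has four: baseline and after each of the three CPTs. The outcomes are identified only by pointing back to earlier text. PGE2 is neither named there nor exempted.

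**The concern.** There are two separate problems.

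First, staff working from the visit text and staff working from the PGE2 paragraph would collect different urine. On the stated 1pm start, the second group would open the collection well after the one challenge that the primary model concerns.

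Second, even with the window settled, the urine described is a single sample for the whole series. It cannot give a value specific to the first CPT, nor separate values for the three CPTs. The time factor for a marker in the primary hypothesis would then have to be chosen outside the written plan.

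**Working it through.** The plan gives no effect size or power figure for PGE2, so there is no PGE2 sample size to reproduce. The IL-6 sizing is not in dispute: 2 × (1.96 + 0.8416)² × (1.71/1.6)² = 17.9, or 18 per group. The exact two-sided t-test gives 19 per group, with 82% power at the planned 20.

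**Step 1: compare the windows.** 1–6pm lasts 5 h and 3–7pm lasts 4 h. They share 3–6pm, which is 3 h. Neither lies inside the other: 1–3pm is only in the first and 6–7pm only in the second.

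**Step 2: place the CPTs.** Inputs from B3.A: start at 1pm, interval 60 min or 1.5 h, immersion 1 min. The table counts immersions.

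| Interval | CPT 1 | CPT 2 | CPT 3 | In 1–6pm | In 3–7pm |
|---|---|---|---|---|---|
| 60 min | 1:00 | 2:00 | 3:00 | 3 of 3 | 1 of 3 |
| 1.5 h | 1:00 | 2:30 | 4:00 | 3 of 3 | 1 of 3 |

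At 60 min the third CPT sits on the window's opening minute. If the interval runs from hand removal, the third CPT moves to 3:02pm or 4:02pm and the counts do not change.

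**Step 3: gap before the 3pm opening.**
- After CPT 1: 3:00 − 1:00 = 2 h.
- After CPT 2: 1 h (60 min interval) or 0.5 h (1.5 h interval).
- Last blood after CPT 1: 1:00 + 1 min + 50 min = 1:51pm, which is 69 min before 3pm.
- At the 1.5 h interval the last blood after CPT 2 is at 3:21pm, so 21 min of that sampling period fall after 3pm.

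**Step 4: what voiding could change.** No void or discard at the window's opening is specified. How much of the urine formed between 1pm and 3pm reaches a 3–7pm collection depends on an assumption:
- Bladder emptied and discarded at 3pm: 0 of 2 h.
- No void from 1pm to 3pm and nothing discarded: 2 of 2 h. If the last void was at 12pm, 1 h of pre-challenge urine is included as well.

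**Step 5: sensitivity to the start time.** If the series in fact began at 3pm, the CPTs would fall at 3:00, 4:00 and 5:00, or at 3:00, 4:30 and 6:00. The 3–7pm window would then hold 3 of 3.

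**Step 6: count model levels.** Inputs: 40 participants with complete data, one baseline urine and one series urine each.

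| Model | Time levels | Values needed | Filled by PGE2 |
|---|---|---|---|
| Primary | 2 | 40 × 2 = 80 | 40 (baseline only) |
| Habituation | 4 | 40 × 4 = 160 | 40 (baseline only) |

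The 40 series values correspond to no stated level. A 1–6pm urine mixes all three CPTs. A 3–7pm urine contains the third and an unknown part of what came before.

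**The case against.** The strongest reply is that 3–7pm is a leftover from an older timetable. The PGE2 paragraph itself refers to the CPT series, and calling a 2pm sample baseline also fits a later start. Each timetable taken alone holds all three CPTs; the count of 1 of 3 arises only when they are crossed. This is plausible, and it is why the conclusion is that coverage is not assured rather than lost. It does not remove the conflict, because the current text gives both instructions.

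Other points stand in part:
- The 20 and 50 min blood times are justified for cortisol and IL-6, and the documents give no excretion timing for the urinary metabolite. The 69 min gap therefore describes the schedule and is not evidence about PGE2.
- A mixed model of baseline versus post-challenge by group can be fitted to the two urines. For the primary objective the failure is that the series value is not a first-CPT value. For habituation the values do not exist.
- That there is only one series urine is inferred from a single start and close time. It is the plain reading, since no separate fractions are described.
- B3.B points back to a set of outcome variables that is not listed as such in the text. Applying both models to PGE2 rests on B1 and on the general references to inflammatory responses in B1 and B2.

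**Conclusion.** The concern holds and should be fixed. The two windows contradict each other, and nothing else in the document settles which applies. With the stated 1pm start, following the PGE2 paragraph means opening the collection 2 h after the first CPT and covering 1 of 3 immersions. Between none and all of the 1–3pm urine is captured, depending on voiding that is not specified.

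Under either window, PGE2 as described fills 1 of 2 levels in the primary model and 1 of 4 in the habituation model. This assumes one baseline and one series urine per participant, and that the B3.B models are meant to cover PGE2.

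The consequence is limited. PGE2 remains usable as a comparison of baseline with series urine between groups; the plan does not say so. IL-6 and cortisol are sampled in blood after every CPT, and the sample size rests on them.

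**What to change.** 1. **Reconcile the windows.** In B3.A, state one challenge-urine window for all participants. It should open with a void just before the first CPT and cover the whole series. Reconcile it in the same edit with the CPT start time, the two stated intervals and the 2pm sample described as baseline. The baseline period, printed as running from 1am to 12pm, also needs a clear time because its urine is the comparator.
2. **Define the analysis.** In B3.B, state that creatinine-adjusted PGE2 is analysed as group by period (baseline urine versus CPT-series urine) and is not part of the first-CPT or habituation models.
3. **Optional.** Both windows include the 5pm pain tests, so describe the PGE2 result as covering the afternoon test period and not the CPTs alone.

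**Cost.** Wording, plus one timed void per participant. No extra assay is needed, provided the baseline urine is already to be assayed for PGE2, as the visit text implies. The price is that PGE2 supports only a whole-series statement and says nothing on habituation; IL-6 still serves both objectives.

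**Alternative.** A timed urine after each CPT would keep PGE2 in both models. It needs three series urines instead of one: (3 − 1) × 40 = 80 more PGE2 assays, each with a creatinine assay. The documents do not show that a 60–90 min urine can resolve a single CPT.

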Visit 1. Initial screening. All potential participants will have the study explained to them in detail by the PI or another senior member of the research team. If interested, potential participants will sign the informed consent and nursing staff in the Clinical Research Center (CRC) will take vital signs and collect a blood sample. A short battery of screening tests and questionnaires will also be collected in order to assess health status and ability to tolerate ice-cold temperatures (a water bath) without adverse circulatory responses. In addition, participants will be asked to record their sleep in the home environment, using sleep diary and actigraphy.

Visit 2. Medical history, physical, and sleep screening. During this visit, urine toxicology and pregnancy (for women)

tests will be performed, and the study physician will meet with the study participant for a physical exam and review of blood test results. Participants who remain eligible following medical screen will be set up with PSG equipment for a sleep screening night in the CRC, in order to rule out any possible sleep disorders.

If a participant has done a screening overnight sleep study within the last 6 months, or a sleep diary recording, screening blood test (including lipid panel, insulin, glucose, TSH, CBC, PLT, CRP, sodium, potassium, billirubin, creatinine, ALT, absolute T Cells, sediment rate), or had a physical examination within the last 3 months, these results will be used for this research.

1-Day CRC Visit: This visit will be scheduled directly following the medical/PSG screen. At 10am, an intravenous (iv) line will be placed for blood drawing. Pain threshold measures (heat and pressure) will be assessed about an hour later. Baseline assessment will begin at 1am lasting until 12pm, during which blood (inflammatory/HPAmarkers), urine (prostaglandin/norepinephinre), and autonomic variables (beat-to-beat blood pressure, heart rate) will be collected. The pain threshold testing will start at 1100am. Following the procedures the heat pain threshold will be assessed by a computer controlled thermode (Somatosensory Analyzer, Medoc, Minneapolis, MS) will be placed on their

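### The only glucocorticoid-sensitivity sample is labelled baseline but timed at 2pm, an hour after the stated 1pm start of the cold pressor series, and the visit's clock times conflict

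*Combined protocol and SAP*

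**What the plan says.** All the timing statements are in B3.A.

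- **GC sensitivity (Procedures).** There is one measurement: "Measures will be performed once at baseline, using the 2pm blood".
- **CPT start.** The visit description says "The reactivity and habituation assessment will take place at 1pm". The CPT paragraph under Procedures agrees: "The CPT will be administered three times during the experimental visit, starting at 1pm".
- **Baseline window (1-Day CRC Visit).** "Baseline assessment will begin at 1am lasting until 12pm". The 1am start precedes the 10am placement of the intravenous line and is evidently garbled.
- **Blood window (Blood Sampling).** Blood is drawn "using an indwelling 18-gauge forearm catheter from 1pm to 7pm". The IL-6 and cortisol paragraphs plan a baseline measure, measures after each CPT, and hourly measures after the last CPT until 7pm.
- **Urine window.** The visit description gives "starting at 1pm and closing out at 6pm". The PGE2 paragraph says the "metabolite will be measured in urine collected during the cold pressor test series (from 3-7pm").
- **Interval between CPTs.** It is 1.5 hours in the visit description and 60 minutes in the CPT paragraph.
- **Pain modulation tests (1-Day CRC Visit).** "temporal summation and conditioned pain modulation will occur at 500pm".

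For secondary objective 2, B3.B compares insomnia and control groups on GC sensitivity at baseline and plans a regression to predict inflammatory reactivity. B1 states the aim as predicting the inflammatory response to challenge from GC sensitivity.

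**The concern.** A baseline comparison and a baseline predictor both need a value taken before the challenge. If the 1pm start and the 2pm draw are both followed, the only GC value is taken after CPT 1, and no earlier sample exists to fall back on.

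The protocol itself gives reasons to care. B2 expects the CPT to raise cortisol and inflammatory cytokines within 15-50 minutes. B1 expects a stronger cortisol response in insomnia. The assay incubates whole blood, which here would be drawn shortly after that window. A group difference in the assay could then partly reflect the groups' different responses to the cold water, rather than the sensitivity they brought to the visit.

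The regression has a related problem. B3.B does not define reactivity for this objective. If it means the CPT 1 response, as in the primary analysis (an assumption), the predictor would be drawn after both bloods that measure the outcome.

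Staff working from this text also cannot tell whether the baseline tube should come before or after the first CPT. If practice varied, samples from both conditions could be pooled under one label.

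**Working it through.** The plan has no figure to reproduce on this point, so the check is a reconstruction of the clock.

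**Inputs (all B3.A).** Immersion lasts 1 minute. Bloods are drawn 20 and 50 minutes after hand removal. The interval between CPTs is 60 or 90 minutes. The GC draw is at 14:00. The stated start is 13:00, and the start implied by the PGE2 urine window is 15:00.

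**Formulas.** CPT k starts at S + (k − 1) × interval. Hand removal is 1 minute later. Bloods fall at removal + 20 and removal + 50 minutes.

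**Stated 1pm start**
- CPT 1: 13:00, removal 13:01, bloods 13:21 and 13:51.
- GC draw after removal: 14:00 − 13:01 = 59 minutes.
- GC draw after the second response blood: 14:00 − 13:51 = 9 minutes.
- GC draw after the stated end of baseline: 14:00 − 12:00 = 2 hours.
- 60-minute interval: CPT 2 is at 14:00, the same time as the GC draw. CPT 3 is at 15:00, with bloods at 15:21 and 15:51.
- 90-minute interval: CPT 2 is at 14:30, 30 minutes after the GC draw. CPT 3 is at 16:00, with bloods at 16:21 and 16:51.

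Under either interval the GC sample is post-challenge.

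**Implied 3pm start**
- GC draw before CPT 1: 15:00 − 14:00 = 60 minutes, so it is pre-challenge.
- 60-minute interval: CPT 3 is at 15:00 + 2 × 60 min = 17:00, with bloods at 17:21 and 17:51.
- 90-minute interval: CPT 3 is at 15:00 + 2 × 90 min = 18:00, with bloods at 18:21 and 18:51.

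**How the remaining times line up**
- For 3pm: the 3-7pm urine window. The 1pm-7pm blood window also fits, because it leaves room for a baseline draw before the series, whereas with a 1pm CPT start it opens only as the challenge begins. Hourly draws until 7pm fit too, although they could also follow a series that began at 1pm.
- Against 3pm: the 1pm start stated twice, the 1pm-6pm urine window, and the 5pm pain modulation tests, since CPT 3 would fall at 5pm or 6pm.

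Neither start time agrees with every statement in the section.

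**The case against.** The strongest reply is that 2pm is a leftover. Taken together, the Procedures paragraphs describe a coherent day: catheter blood from 1pm, baseline blood at 2pm, the series from 3pm, and the last draw at 7pm. Both the GC paragraph and B3.B use the word baseline, so a pre-challenge sample was plainly meant, and a single stale clock time is a simpler explanation than planned post-challenge sampling. Figure 1, cited at the start of B3.A, may show the intended timeline but could not be seen in the text reviewed.

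Much of this stands. The 3pm reading has real support, and a reader should not infer that the plan chose to sample after the challenge; no section says so. But the reading does not repair the text, because it contradicts the other times set out above. A figure could show what was intended, yet the conflicting sentences would remain.

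Nor should a reader infer that the 5pm pain tests rule out a 3pm start. Blood is planned until 7pm, so draws after 5pm are expected. The 5pm tests show only that the schedules conflict.

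A second reply is that the harm is conjectural. The 15-50 minute range in B2 concerns circulating markers, not monocyte sensitivity in vitro, and 59 minutes lies just outside it. That is correct, and it limits the conclusion to a possible bias.

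**Conclusion.** The point holds as an internal inconsistency. Followed literally, the stated times put the only GC-sensitivity sample 59 minutes after CPT 1 hand removal, assuming the full 1-minute immersion, while the plan labels and analyses it as baseline. The conflict in the text is certain; which time was intended is not.

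It might be inferred that the GC result is biased. The documents do not support that: they do not say whether the CPT changes the assay, or by how much, so no effect on estimates or error rates can be given.

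For this sample, the consequence is confined to secondary objective 2. The sample size of 20 per group and the mixed model for the primary objective do not use the assay. The other timing conflicts reach further: the two urine windows bear on PGE2, a marker under the primary objective, and the two intervals bear on habituation, secondary objective 1. The point should be fixed, but it does not undermine the trial's main comparison.

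**What to change.** In the GC paragraph of B3.A, replace the reference to 2pm blood with: *the baseline blood drawn before the first CPT of the experimental visit*. The last four words are needed because a trial CPT is also given at screening. Record the actual draw time for each participant, and do not label or analyse as baseline any sample drawn after that first CPT. This wording holds whichever schedule is confirmed.

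Separately, reconcile the remaining times in B3.A:
- the CPT start and the baseline window, including the garbled 1am and the blood window that opens only at 1pm;
- the urine windows (1pm-6pm against 3-7pm);
- the interval between CPTs (60 minutes against 1.5 hours).

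The sponsor must say which times apply; the documents do not settle it.

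The cost is a wording change. The assay is still run once, and the tube can come from the baseline blood already planned for IL-6 and cortisol.
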